6.2.3. Sensitivity Analyses for the Primary Variable

The following list of sensitivity analyses are pre-specified for this study, with an aim toward assessing the robustness of the primary efficacy results:

- The primary analysis with offset variable calculated as the logarithm of follow-up duration (ie, not excluding the summed duration of exacerbations).
- The primary analysis with control variables for age and blood eosinophil categories based on data recorded in the IRT (as randomized). This analysis will only be

performed if the number of discrepancies between data recorded in the IRT and the clinical database are sufficiently large (eg, 5% of total population).

- **On-treatment:** analysis of the primary endpoint including exacerbations during the treatment period (ie, observed until treatment completion or until withdrawal from treatment, excluding any exacerbations observed after withdrawing from treatment).
 - For patients who complete treatment, the treatment period will be defined from the first dose of study drug to the end of treatment (week 52) visit. For patients who prematurely discontinue treatment, the treatment period will be defined from the first dose of study drug to the last dose of study drug + 4 weeks.
- **Per-protocol:** on-treatment analysis of the primary endpoint including exacerbations during the treatment period (ie, observed until treatment completion or until withdrawal from treatment, excluding any exacerbations observed after withdrawing from treatment), based on the PP analysis set.
- **“Tipping point” multiple imputation:** analysis of the primary endpoint to assess deviations from missing at random (MAR). The details regarding this analysis are provided in [Appendix B](#).

6.2.4. Component Analysis for the Primary Variable

The frequency of the following individual components of the composite CAE definition will be examined separately.

- asthma exacerbations requiring use of systemic corticosteroids (oral or injection) or at least a doubling from a stable maintenance oral corticosteroid dose for at least 3 days
- asthma exacerbations requiring either hospitalization or emergency department visit

The following individual components will also be examined, however due to the low event rates expected, these events will only be presented descriptively.

- asthma exacerbations requiring hospital admission
- asthma exacerbations requiring an emergency department visit

These analyses will be restricted to on-treatment events.

6.2.5. Subgroup Analysis for the Primary Variable

The primary efficacy variable will additionally be examined for the subgroups defined in Section 3.4. The analysis will be similar to the on-treatment analysis described for the primary endpoint (Section 6.2.3). An interaction p-value will be derived from a separate NB model including additional terms for subgroup and treatment by subgroup interaction. Subgroup analyses for the primary efficacy variable will be presented graphically using forest plots.

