#### **4.4.1. Discontinuation of Study Treatment**

If premature discontinuation of study treatment occurs for any reason, the patient should continue attending remaining study visits while off study treatment. The patient should not be considered withdrawn from the study due to interruption or discontinuation of study treatment. For this study, it is very important to continue collecting data from all patients whether or not they complete treatment.

If premature discontinuation of study treatment occurs, the patient should return to the clinic as soon as possible for a study treatment discontinuation visit. All evaluations should be performed as an unscheduled visit and include all the assessments specified in the protocol for the early withdrawal visit (see Table 2). The investigator must determine the reason for and the date of discontinuation of study treatment and record this information in both the source documentation and the Study Drug Treatment Completion CRF. The patient's continued participation in the study must be discussed by the investigator and site staff with the patient; the investigator and site staff must also request the patient to continue attending study visits according to the study visit schedule with all assessments completed up to week 52 (visit 17). The CAE event status and safety assessments at week 52 (visit 17) are the priority assessments for patients that prematurely discontinue study treatment. At a minimum, the investigator should make every effort to obtain information regarding serious adverse events, CAE events, and survival status at week 52. A safety follow-up visit (visit 18) should be conducted 12 weeks after visit 17.

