### **9.1. Sample Size and Power Considerations**

The primary efficacy variable for this study is the frequency of CAEs per patient during the 52-week treatment period. The study will be considered positive if the primary efficacy measure indicates a statistically significant treatment effect of reslizumab versus placebo at the respective predefined significance level.

Power calculations were based on the below assumptions:

- Negative binomial (NB) distribution for the number of exacerbations with a mean of 2.9 exacerbations per patient per year for the placebo group
- Dispersion parameter of 1.2
- Treatment effect of 45% between the reslizumab group and the placebo group
- Alpha level of 0.05

Based on the assumptions above, 225 patients per arm (450 total) will provide >90% power to detect significant treatment effect of reslizumab over placebo in the reduction of exacerbation rate. The sample size was increased beyond the sample size required to provide 90% power in order to allow sufficient number of patients to assess safety and immunogenicity and to ensure adequate enrollment in the adolescent subset. The current sample size also provides higher power for other efficacy endpoints.

Patients with blood eosinophil levels of 300/ $\mu$ L to <400/ $\mu$ L will be limited to no more than 30% of patients (60 patients per treatment group).

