#### **9.5.6.1. Primary Efficacy Analysis**

The primary analysis of frequency of CAEs will use the NB regression model. The primary NB model will include the treatment group, randomization stratification factors, and number of exacerbations in the previous year as model factors and an offset variable. The offset variable will be calculated as the logarithm of follow-up duration minus the summed duration of exacerbations. The ratio of CAE rate between the treatment groups and its 95% confidence interval (CI) will be estimated from the NB model.

CAEs that occur between the completion of the 1st dose of study drug and 2 weeks after the end of treatment/early withdrawal visit will be counted towards the CAEs for analysis.

The primary analysis will incorporate data from all randomized patients. The analysis will include the frequency of all exacerbations observed in 52 weeks, for patients completed the 52 weeks treatment period and for patients withdrew from treatment earlier than 52 weeks. For early withdrawal patients that the sponsor will fail to retrieve data after withdrawal despite all

attempts to contact the patient, a multiple imputation will be performed for the frequency of exacerbation after withdrawal. The multiple imputations will utilize the post-withdrawal data observed for patients who withdrew early and for which the sponsor succeeded to retrieve the data. The methodology and algorithm to be used for imputations will be detailed in the Statistical Analysis Plan.

Sensitivity analyses will include:

- Analysis including the frequency of all exacerbations observed until treatment completion or until withdrawal from treatment, excluding exacerbations observed after withdrawing from treatment.
- Repeating the primary analysis using an offset variable in the NB model calculated as the logarithm of total follow-up duration (not excluding the summed duration of exacerbations).
- Repeating the primary analysis on the Per-protocol analysis set.
- “Tipping point” multiple imputation analysis to assess deviations from missing at random (MAR). The details regarding this analysis will be provided in the SAP.

Additional sensitivity analyses will be detailed in statistical analysis plan.

In addition, to the analysis described above, subgroup analyses will be performed for:

1. Age categories. Patients at ages 12 to <18 and patients  $\geq 18$  will be analyzed separately.
2. [REDACTED]

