3.1. Intent-to-Treat Analysis Set

The intent to treat (ITT) analysis set will include all randomized patients, with the exception of patients from Site [REDACTED] who will be excluded. In this population, treatment will be based on the treatment to which patients were randomized, regardless of which treatment they actually received.

Two analytic approaches are planned using the ITT analysis set.

- In the first approach, all data collected from patients will be included, regardless of continued adherence to their assigned study treatment.
- In the second approach, data collected from patients during the treatment period will be included, up to the point at which patients discontinue from their assigned study treatment (on-treatment). For patients who completed treatment in this study, the treatment period will be defined from the first dose of study drug to the end of treatment (week 52) visit. For patients who prematurely discontinue treatment, the treatment period will be defined from the first dose of study drug to the last dose of study drug + 4 weeks.

The analytic approach including all data collected from patients will be utilized as the primary approach to analysis for the primary endpoint (frequency of CAE). The on-treatment approach will be conducted as a sensitivity analysis for the primary endpoint. For the analysis of all other efficacy endpoints, the on-treatment approach will be utilized as the main approach to analysis. The analytic approach including all data collected from patients will additionally be conducted as sensitivity analyses for selected secondary endpoints.

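### SAP 6.2.5 bases all CAE subgroup and interaction analyses on on-treatment events, although the primary CAE analysis uses all data

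*SAP*

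**What the plan says.** SAP 3.1 describes two ways of using the ITT data. The approach including "all data collected from patients will be utilized as the primary approach to analysis for the primary endpoint", and the on-treatment approach is a sensitivity analysis for that endpoint.

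SAP 6.2.2 (the primary analysis) counts CAEs over 52 weeks on or off drug, up to two weeks after the end-of-treatment or early-withdrawal visit. Post-withdrawal counts that cannot be retrieved are multiply imputed. SAP 6.2.3 (on-treatment) stops at the week 52 visit for completers and at last dose plus 4 weeks for early stoppers, and drops later CAEs.

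SAP 6.2.5 states: "The primary efficacy variable will additionally be examined for the subgroups defined in Section 3.4", and then "The analysis will be similar to the on-treatment analysis described for the primary endpoint (Section 6.2.3". It continues: "An interaction p-value will be derived from a separate NB model including additional terms for subgroup and treatment by subgroup interaction". Forest plots follow. No other data scope is named. Section 3.4 includes the age strata (3.4.1) and eosinophil strata (3.4.2). Additional all-data analyses are foreseen only for selected secondary or by-visit variables (SAP 3.1, 4.5, 6.3).

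Protocol 9.5.6.1 sets out the all-data primary analysis and its sensitivity analyses. It then says "In addition, to the analysis described above, subgroup analyses will be performed for" and lists the age and eosinophil categories without limiting them to on-treatment events. Protocol 4.4.1 stresses that "it is very important to continue collecting data from all patients whether or not they complete treatment".

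**The concern.** A subgroup analysis of the primary endpoint is normally read against the primary result: does the same effect appear here? That reading needs the same estimand. Here the headline rate ratio reflects assignment to reslizumab over the full year, including time after stopping. The subgroup ratios and interaction p-values reflect only time on drug plus four weeks.

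Two subgroups matter most. Protocol 9.1 gives as one reason for the sample size "to ensure adequate enrollment in the adolescent subset". The 300 to <400/µL stratum lies below the ≥400/µL threshold of the earlier positive intravenous studies (Protocol 1.3.2.2). Two consequences are possible:
- Subgroup ratios could look more favourable than the primary result even when the true effect is identical everywhere.
- A difference between subgroups that arises through unequal discontinuation would be invisible on-treatment.

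The data that the protocol takes trouble to collect after stopping would play no part in either.

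**Working it through.** **Inputs from the documents (SAP 2.3, 4.3; Protocol 9.1).** Placebo rate 2.9 CAEs per year, rate ratio (RR) 0.55, dispersion 1.2, two-sided alpha 0.05, 225 per arm, at most 60 per arm in the lower eosinophil stratum. **Assumed:** share of early stoppers, timing of stopping, and waning of benefit. The documents give none of these for this trial.

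**1. The plan's own figure.** Variance of log RR = (1/2.9 + 1.2 + 1/1.595 + 1.2)/n = 3.372/n. At n = 225 the SE is 0.1224; |ln 0.55| = 0.598; 0.598/0.1224 − 1.96 = 2.92, so power is 99.8%. This agrees with >99% (Protocol synopsis) and >90% (SAP 2.3, Protocol 9.1). No stated figure is in dispute.

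**2. All-data ratio with gradual waning.** Assume last doses of stoppers uniform over weeks 0 to 44, full benefit to last dose + 4 weeks, then linear loss to none at 17.3 weeks (4 months) after last dose. The time left after the on-treatment cut-off, u, is then uniform on 4 to 48 weeks. Benefit lost, in placebo-equivalent weeks, is 0.45 × u²/26.6 for u ≤ 13.3 and 0.45 × (u − 6.65) beyond. The mean of the bracketed part is (28.7 + 832.8)/44 = 19.6 weeks. As a share of the year, 0.45 × 19.6/52 = 0.169. Hence all-data RR = 0.55 + 0.169 × p, where p is the share of stoppers:

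| Stoppers p | On-treatment RR | All-data RR | Excess of the 45% reduction over the all-data reduction |
|---|---|---|---|
| 10% | 0.55 | 0.567 | 4% |
| 15% | 0.55 | 0.575 | 6% |
| 20% | 0.55 | 0.584 | 8% |
| 25% | 0.55 | 0.592 | 10% |
| 30% | 0.55 | 0.601 | 13% |

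At 20% stoppers, about 10% of placebo and 15% of reslizumab CAEs within 52 weeks are left out.

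**3. Cross-check.** A simulation with stopping uniform over the year, a 4-week tail and immediate return to the placebo rate gives 0.568, 0.588 and 0.609 at 10%, 20% and 30% stoppers.

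**4. Size against noise.** At 60 per arm the SE of log RR is √(3.372/60) = 0.237. The shift is ln(0.567/0.55)/0.237 = 0.13 SE at 10% stoppers and ln(0.584/0.55)/0.237 = 0.25 SE at 20%.

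**5. Interaction.** With off-treatment person-time share f and off-treatment ratio r, all-data RR = 0.55(1 − f) + f × r. Take r = 1 and f = 5% in one subgroup, 20% in the other: 0.573 and 0.640, a ratio of ratios of 1.12. On-treatment it is 1.00. This is a strong contrast: in the simulation of step 3, 30% stoppers produce only 12.8% off-treatment time. For 60 versus 165 per arm the SE of the log ratio of ratios is √(3.372/60 + 3.372/165) = 0.277, so 1.12 is about 0.4 SE. With f = 5% and 10% the ratio of ratios is 1.04.

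**The case against.** The case for leaving the SAP alone has real substance.

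- **Protocol.** A reader might infer an undeclared breach of Protocol 9.5.6.1, since SAP Section 10 reports no changes to protocol analyses. The documents do not support that. The protocol gives no data scope for the subgroups, Protocol Section 9 leaves details to the SAP, and the SAP preface says the SAP prevails. The mismatch is between the subgroup analyses and the primary estimand that both documents set.
- **Role.** Subgroups lie outside the fixed testing sequence and have no multiplicity control (SAP 4.3). Neither document attaches a formal adolescent or low-eosinophil efficacy claim to them. This stands, and the primary test is unaffected.
- **Consistency.** It is tempting to say that consistency across subgroups is never tested. It is tested, on on-treatment CAEs, and an overall on-treatment analysis (SAP 6.2.3) supplies a like-for-like reference. What is missing is the test on the primary estimand.
- **Why patients stop.** Protocol 3.14 names lack of efficacy and adverse events, but as reasons for leaving the study, not for stopping drug while staying in it. It does not show that the cut-off is driven by outcome.
- **Waning.** The four-month figure comes from mean eosinophil counts at follow-up in earlier studies (Protocol 1.3.2.2). It is not a CAE offset curve for 110 mg subcutaneously.
- **Imputation.** Appendix A imputes from early stoppers with complete follow-up (ET1), by arm only. Simply subsetting those datasets would give every subgroup the same arm-level imputed rate and pull the estimates together. This shapes the fix.

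**Conclusion.** The mismatch stands on the text: the primary result uses all data, and every CAE subgroup ratio, forest plot and interaction test uses on-treatment events, with no all-data version planned.

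Its size is conditional. Under the waning assumption, 0.55 on-treatment compares with about 0.57 to 0.60 all-data at 10 to 30% stoppers. In a stratum of 60 per arm that is 0.13 to 0.25 SE at 10 to 20% stoppers. The gap is zero if benefit persists off drug or nobody stops. It would therefore go too far to say that the subgroup results will overstate the effect. The interaction point likewise needs discontinuation to differ between subgroups. Even then the shift is small against the test's precision, so the issue is what the test estimates more than what it would detect.

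The case for changing the plan rests on matching the subgroup evidence to the primary estimand at low cost.

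**What to change.** In SAP 6.2.5, for at least the age and eosinophil strata:

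1. Prespecify the subgroup and treatment-by-subgroup analyses of CAE frequency on the all-data approach of 6.2.2, with the primary result as the overall row of the forest plot.
2. Keep the on-treatment subgroup analysis as supportive, with its own on-treatment overall row.
3. State how missing post-withdrawal data are handled. Either add the stratum to the Appendix A imputation model where the number of ET1 patients allows, or use all observed CAEs and follow-up, on and off treatment, with the log follow-up offset and no imputation. In the second case, add an overall row fitted the same way. State that arm-level imputation shrinks subgroup differences.
4. Exclude the ADA subgroup, which covers reslizumab-treated patients only (SAP 3.4.5), from rate-ratio comparisons.

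The cost is SAP wording and modest programming, with no new data. Interaction tests must be pooled over imputations if imputed data are used, and intervals in small strata may be slightly different or wider.

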6.2.6. Time to First Clinical Asthma Exacerbation

The Kaplan-Meier (KM) method will be used to estimate and compare the distributions of time to first CAE between treatment groups. Time to first event will be analysed for on-treatment events.

The time period for the on-treatment analysis will extend from the date of first dose of study drug to the cessation of study treatment, defined as the date of the end of treatment (week 52) visit for patients who completed treatment and the date of last dose (+4 weeks) for patients who discontinued treatment early. Patients without an event during the treatment period will be censored at either the date of the end of treatment (week 52) visit for patients who completed treatment or at the date of last dose (+4 weeks) for patients who discontinued early.

The hazard ratio (95% CI) and p-value will be estimated using a Cox proportional hazards regression model adjusting for the stratification factors.

The following sample SAS[®] code pertains to the analysis of time to first CAE.

```
proc lifetest data=<<>> outsurv=<<>>;
  time ttcae*censor(0);
  strata treatment;
  ods output quartiles=<<>>;
run;

proc phreg data=<<>>;
  class treatment (ref='PBO');
  model ttcae*censor(0) = treatment / rl ties=discrete;
  strata strata1 strata 2;
  ods output parameterestimates=<<>>;
  ods output globaltests=<<>>;
run;
```

A KM plot will be provided for the time to first CAE by treatment group.

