#### **3.16.4. Procedures After Study Drug Treatment**

Patients who participate in the study in compliance with the protocol for at least 52 weeks of double-blind treatment will be considered to have completed the treatment period. Patients who complete the follow-up visit (week 64) will be considered as having completed the study. An exception to this may be adult patients who enroll in an available open-label, long-term safety study and complete the early and late follow-up visits as part of that study. These adult patients may be considered as having completed the current study at the time of the 52-week visit (end of treatment period). See Section 12.4 for the definition of the end of the study.

For patients who complete the treatment period, final evaluations will be performed at the end-of-treatment/week 52 visit and the follow-up visit.

Patients who discontinue treatment prematurely must be encouraged to continue to attend the regular scheduled visits, and complete the prescribed safety and efficacy evaluations through the end-of-treatment/early withdrawal visit and the follow-up visit, if at all possible (see Section 4.4).

Patients who both discontinue treatment and also withdrawal from the study should have final evaluations performed on the last day the patient receives the study drug, or as soon as possible thereafter. The patient should also return for the follow-up visit and procedures if at all possible (see Section 4.4).

Procedures for patients who withdraw prematurely from the study are described in Section 4.4. Following termination of the study, patients should be treated according to the standard of care, and as guided by the Principal Investigator.

Patients with ongoing adverse events or clinically significant abnormal laboratory test results (as interpreted by the investigator) will be monitored as described in Section 7.1.2.

The following procedures/assessments will be performed at the follow-up visit (EOT +12 weeks ±14 days, end of study visit):

- Perform hematology tests.
- Assess asthma exacerbations and related health care utilizations.
- Collect blood for serum reslizumab concentration determination (PK assessment) from all patients.
- Collect blood sample for immunogenicity (ADA) assessment.
- Perform adverse event inquiry.
- Perform concomitant medication inquiry.
- Perform urine pregnancy test.

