#### **4.4.2. Complete Withdrawal from Study**

If a patient decides to completely withdraw from the study (ie, refuses any further study participation or contact), all study participation for that patient will cease and all data to be collected at subsequent visits will be considered missing. If a patient decides to completely withdraw from the study, the patient should return to the clinic as soon as possible to complete the early withdrawal visit (see Table 2). A complete final evaluation at the time of the patient's withdrawal should be made, including an explanation of why the patient is withdrawing from the study. The reason for and date of withdrawal from the study must be recorded in the source documentation and the Double-Blind Treatment Period Completion CRF.

For patients who are lost to follow-up (ie, patients whose status is unclear because they fail to appear for study visits without stating an intention to withdraw), the investigator should make appropriate efforts to re-establish contact with patient; attempts to contact the patient should be documented in the source documents. If contact has not been re-established, efforts should still be made to locate the patient and obtain information regarding serious adverse events, CAE

events, and survival status at the end of the 52-week treatment period. A patient should only be designated as lost to follow-up if the site is unable to establish contact with the patient after 3 documented attempts via 2 different methods (phone, text, e-mail, certified letter, etc).

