6.3. Secondary Efficacy Variable(s) and Analysis

As described previously in Section 4.5, an on-treatment approach will be adopted as the primary analysis for the efficacy variables assessed by-visit. In this analysis, the treatment period will be defined from the first dose of study drug to the end of treatment (week 52) visit for patients who completed treatment and from the first dose of study drug to the last dose of study drug (+4 weeks) for patients who discontinued treatment early. Measurements collected outside of these defined timeframes will be excluded from the analyses and endpoint will be defined within these timeframes. All results will be included in the patient listings. For selected key variables, additional sensitivity analyses may also be performed in which all post-baseline measurements collected during the study will be included and endpoint will be defined within this extended timeframe.

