6.3.9.2. Analysis

Compliance with the daily diary assessments will be derived for each patient as an additional measure of protocol adherence. A diary compliant day will be defined as a day with non-missing values for all diary assessments, including AM/PM asthma symptom score, [REDACTED],

[REDACTED]. Diary compliance will be derived as a percentage over the treatment period:

- $\text{Diary compliance (\%)} = 100 \times (\text{total number of diary compliant days} / \text{total number of days during the treatment period})$

The treatment period for diary compliance extends from the first day of study drug to the last day of study drug. Note that, in this analysis, missing data will be treated as non-compliant (eg, if compliance cannot be assessed for a given day due to missing data, then the day will not be counted as a diary compliant day).

[REDACTED]

A weekly average of the daily diary measures ([REDACTED], total asthma symptom score, and [REDACTED]) will be derived (see [Table 3](#) for the definition of analysis days for diary data). The average will be calculated as the sum of all values divided by the number of non-missing assessments. There will be no imputation of missing data. At least 4 of the 7 measurements need to be recorded for a week to be included in the analysis; otherwise the week will be treated as missing.

[REDACTED] and asthma control days will be derived and analyzed as percentages over the relevant analysis period, derived as:

- $\text{Asthma control days (\%)} = 100 \times (\text{total number of asthma control days} / \text{total number of days during the analysis period})$

[REDACTED]

The analysis periods are as defined in [Section 6.3](#). Note that, in this analysis, missing data will be treated as non-responders (eg, if asthma control cannot be assessed for a given day due to missing data, then the day will not be counted as an asthma control day).

Summary statistics of actual values and change from baseline to each week will be provided by treatment group.

Analysis of the change from baseline to each week will use a similar MMRM model as described in [Section 6.3.3.2](#) with the exception of inclusion of sex and height in the model.

Analysis of the percentage of [REDACTED] and percentage of asthma control days will be performed using an analysis of variance (ANOVA) model with fixed effects for treatment, age group, and blood eosinophil counts at enrollment.

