7.2. Study Drug Administration

The exposure to study drug will be characterized by duration of treatment and by the number of patients receiving at least 1, 2, 3, etc. injections. Total patient years will also be summarized. The summaries will be provided by treatment group and overall, and by baseline stratification factors.

Duration of treatment period is defined separately for patients who completed/discontinued treatment.

- Completed: End of treatment (week 52) visit date – first dose date + 1
- Discontinued: Last dose date – first dose date + 29

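### Time to first CAE censors event-free early stoppers at last dose + 4 weeks even if they left the study sooner, so up to 28 unobserved days each count as CAE-free follow-up

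*SAP*

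**What the plan says.** SAP 6.2.6 restricts time to first CAE to on-treatment events and censors event-free patients at the week 52 visit "for patients who completed treatment or at the date of last dose (+4 weeks) for patients who discontinued early". The window is the same elsewhere. For premature discontinuation, SAP 3.1 states that "the treatment period will be defined from the first dose of study drug to the last dose of study drug + 4 weeks". SAP 6.3 runs it "from the first dose of study drug to the last dose of study drug (+4 weeks) for patients who discontinued treatment early", and SAP 4.5 and 6.2.3 agree. None of these sections mentions study exit or last contact.

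For asthma control days, SAP 6.3.9.2 takes its analysis period from 6.3 and divides by all days in that period. It adds that "missing data will be treated as non-responders (eg, if asthma control cannot be assessed for a given day due to missing data", such a day is not counted as controlled).

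Stopping drug and leaving the study are separate events in the protocol. Under 4.4.1, patients who only stop drug keep attending visits. Under 4.4.2, after complete withdrawal "all study participation for that patient will cease and all data to be collected at subsequent visits will be considered missing". Under 3.16.4, patients who do both "should have final evaluations performed on the last day the patient receives the study drug, or as soon as possible thereafter".

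**The concern.** Dosing is every 4 weeks. A patient who leaves x days after the last dose, with x below 28, is carried for 28 − x further days with no observation. In time to first CAE those days are event-free time at risk. In asthma control days the same days are failures. An arm with more exits is therefore flattered on one endpoint and penalised on the other.

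This does not fit the SAP's own principles. Section 4.4 says that endpoints other than the primary use observed data only. Appendix A treats the unobserved time of patients who leave the study as missing exposure, to be imputed. Section 5.2 plans Kaplan-Meier plots to look for differential dropout, so unequal loss is a possibility the sponsor already has in mind.

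Asthma control days is fifth and time to first CAE seventh among the nine secondary endpoints in the fixed sequence, so both can carry a formal claim.

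**Working it through.** **Inputs from SAP 2.3.** Placebo rate 2.9 per year, dispersion 1.2, 45% reduction (reslizumab rate 2.9 × 0.55 = 1.595), two-sided 0.05, 225 per group. Exit rates, exit timing and the true percentage of control days are not in the documents. They are assumptions here.

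**The plan's own figure.** Var(log rate ratio) = (1/2.9 + 1/1.595 + 2 × 1.2)/225 = 3.372/225 = 0.01499, so SE = 0.1224. |ln 0.55| = 0.598, and 0.598/0.1224 − 1.96 = 2.92, which gives power of 99.8%. This agrees with the SAP (>90%) and the protocol synopsis (>99%).

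**Are the gap days really low-risk?** The chance of at least one CAE in 28 days is 1 − (1 + 1.2 × 2.9 × 28/365)^(−1/1.2) = 0.18 on placebo, and 0.11 at 1.595 per year. This concerns only leavers' unobserved days, and it is lower for patients who have already gone some time without an event.

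**Amount of unobserved time.** If exit is uniform between doses, the mean gap is 14 days. At 10% exit that is 22.5 patients × 14 = 315 days per 225 patients, about 0.4% extra time at risk (0.8% if all exits fall just after a dose).

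**Closed form for asthma control days.** A leaver after dose k has a window of 28k days, of which on average 14 are unobserved, a fraction 1/(2k). Averaged over doses 1 to 13: (1 + 1/2 + … + 1/13)/13 = 3.180/13 = 0.245, and half of that is 0.122. With true control of 50% in both arms, the arm mean falls by 50 × exit rate × 0.122. That is 1.22 points at 20% and 0.61 at 10%, a spurious difference of 0.61. If all exits fall just after a dose, the fraction is close to 1/k and the difference roughly doubles.

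**Simulation.** Gamma frailty with dispersion 1.2, first CAE at the planning rates, 28-day dosing, 400,000 patients per arm. Each data set was analysed with the window as written and with the window cut at exit. A hazard ratio near 0.69 is what a rate ratio of 0.55 becomes for first events under this heterogeneity.

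| Exit, placebo / reslizumab | Exit timing | HR as written | HR cut at exit | Spurious difference in asthma control days, as written (points, reslizumab − placebo) |
|---|---|---|---|---|
| 10% / 10% | uniform | 0.686 | 0.686 | 0.0 |
| 20% / 10% | uniform | 0.689 | 0.686 | +0.6 |
| 20% / 10% | just after a dose | 0.689 | 0.683 | +1.2 |
| 10% / 20% | uniform | 0.681 | 0.684 | −0.6 |
| 10% / 20% | just after a dose | 0.677 | 0.682 | −1.2 |
| 30% / 10% | uniform | 0.690 | 0.684 | +1.2 |
| 30% / 10% | just after a dose | 0.697 | 0.684 | +2.4 |

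With equal exit of 5%, 10% or 20%, the two hazard ratios agree to within 0.0002. At 20% / 10% with uniform timing, the asthma-control-day artefact is 0.4 points if true control is 30%, and 0.8 if it is 70%.

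**Against sampling error.** Without exits, the chance of a first CAE in 52 weeks is 71% on placebo and 59% on reslizumab, so about 293 events in 450 patients. SE(log HR) is then about √(4/293) = 0.117. The uniform 20% / 10% shift is ln(0.6887/0.6858) = 0.004, or 0.04 SE. Just after a dose it is ln(0.6889/0.6827) = 0.009, or 0.08 SE. For asthma control days the documents give no SD. Assuming 25 to 45 points, the SE of the difference, SD × √(2/225), is 2.4 to 4.2 points, so 0.6 points is about 0.14 to 0.25 SE.

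**The case against.** The case against has several parts.

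- **The gap is often short or absent.** Patients who stop drug but stay are observed throughout. SAP 4.5 accepts early-termination data 3 to 5 weeks after the last dose, so some exits will fall close to the end of the window. This stands, and it is why exits just after a dose are treated as the upper case only.
- **CAE status may be known after exit.** Protocol 4.4.1 and 4.4.2 ask for efforts to obtain it at week 52 for treatment stoppers and for patients lost to follow-up. This also stands. Where those efforts succeed, the days are observed and the censoring date need not change. They do not cover patients who refuse further contact, and they cannot recover diary entries.
- **Scoring missing diary days as failures is a declared choice.** That is true for days while the patient is in the study. What the SAP neither states nor justifies is carrying the rule past study exit.
- **Cutting the denominator has its own problem.** A patient who leaves on the first dosing day would have no days, giving 0/0, and a randomised patient would drop out of the analysis. This stands, and it is why the change is offered as a sensitivity analysis with explicit rules.

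A reader might also infer that exposure in SAP 7.2 is inflated, because duration for discontinued patients is "Last dose date – first dose date + 29". The documents do not support that. The formula defines treatment duration, not observation, and the protocol gives a half-life of about 26 days after subcutaneous dosing. A reader might likewise conclude that the on-treatment negative binomial analyses are affected. The SAP calls their offset follow-up duration and does not say that unobserved days enter it.

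**Conclusion.** The gap in SAP 6.2.6 is real on the text but minor in effect. Bias between arms needs unequal complete withdrawal, for which the documents give no rates. Across the scenarios tried, the hazard ratio moves by less than 0.01, except at 30% versus 10% exit with every exit just after a dose (0.697 against 0.684). For asthma control days the figure is 0.6 to 1.2 points at 20% versus 10% exit, assuming 50% true control.

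It would be tempting to say that the rule manufactures a benefit for reslizumab. It does not do so in general. If placebo loses more patients, asthma control days tilt towards reslizumab while time to first CAE tilts against it. If reslizumab loses more, both directions reverse. It would also be wrong to extend the point to the primary analysis, which uses all collected data and multiply imputes the missing exposure of patients who left.

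**What to change.** 1. **SAP 6.2.6.** Censor event-free early stoppers at the earlier of last dose + 4 weeks and the last date on which CAE status is known. That date is study withdrawal or last contact, and includes any CAE status retrieved after exit.
2. **SAP 6.2.3 and 6.2.7.** State what follow-up duration means for early stoppers. If the offset uses the same window, end it at the same date.
3. **SAP 6.3.9.2.** Keep the planned analysis. Add a sensitivity analysis whose denominator ends at study exit, with a stated minimum number of days and a rule for patients with no post-dose diary days. Keep the non-responder rule for days while the patient is in the study.

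The cost is a clause or two in the SAP, one derived date and one extra table. Protocol 4.4.2 puts the withdrawal date on the Double-Blind Treatment Period Completion CRF. It describes no last-contact field for patients lost to follow-up, so their date would have to be derived, for example from the last visit attended, since exacerbations are assessed at every treatment-period visit. The change should be settled before unblinding, because a later change to two endpoints in the testing sequence would look data-driven.
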